Age-related Macular Degeneration (AMD) in the Vitamin D and Omega-3 Trial (VITAL)

NCT01782352

(3/29/2012)

Protocol: AMD in the VITamin D and OmegA-3 TriaL (VITAL)

(Version 1: 3/29/2012)

I. BACKGROUND AND SIGNIFICANCE

Age-related macular degeneration (AMD) is the leading cause of blindness in the US. An estimated 1.75 million US men and women suffer from the advanced forms of geographic atrophy or neovascular AMD, and another 7 million are at substantial risk of this outcome. 1 Despite advances in photodynamic 2 and antivascular endothelial growth factor therapy^{3, 4} for patients with neovascular AMD, and the demonstration of benefit from a supplement of antioxidants plus zinc for people with intermediate to advanced AMD,⁵ vision loss from AMD remains commonplace. **VITAL-AMD** will use the resources of the **VIT**amin D and Omeg**A**-3 Tria**L** (**VITAL**) (U01 CA138962; [name], PI) to test the efficacy of two promising preventive agents in delaying the incidence and progression of AMD among 20.000 older men and women. Vitamin D3 and omega-3 fatty acids share anti-inflammatory, antioxidant, antiproliferative, and antiangiogenic properties, and evidence supports potential benefits of both agents as strong candidates for prevention of AMD. VITAL-**AMD** will have strong statistical power to address the primary (incidence) and secondary (progression to advanced stages) prevention of AMD. Findings from this study will clarify whether these agents reduce incidence and progression of AMD, and will provide important data for both public health and clinical guidelines for the primary and secondary prevention of AMD.

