- 6. Are there associations of polymorphisms in CYP24A1, vitamin D receptor, desaturase genes, or other genes with functional relevance to vitamin D and omega-3 fatty acid pathways with incidence of AMD?
- 7. Do polymorphisms in CYP24A1, the vitamin D receptor, complement factor H, ARMS2, C3, C2/BF, RORA, or other functionally relevant genes modify the effects of vitamin D3 on the AMD endpoints?
- 8. Do polymorphisms in desaturase genes (FADS1, FADS2, FADS3), elongase of very long fatty acids 2 (ELOVL2), complement factor H, ARMS2, C3, C2/BF, RORA, or other functionally relevant genes modify the effects of EPA+DHA on the AMD endpoints?

Secondary aims 6, 7, and 8 will be addressed in the subgroup which provides a baseline blood specimen using a nested case-control sample of all AMD cases (incident AMD cases and progression to advanced AMD) and a set of age- and sexmatched controls remaining free of AMD.

III. SUBJECT SELECTION/ENROLLMENT

VITAL-AMD is an ancillary study of the NIH-funded **VITAL** trial. All persons randomized in **VITAL** are included in this ancillary study.

Individuals are eligible for *VITAL* trial participation if they meet the following criteria: (1) are age ≥60 (men) or ≥65 (women); (2) have at least a high school education (to complete mail-based questionnaires); (3) have no history of cancer (except non-melanoma skin cancer), MI, stroke, TIA, angina pectoris, CABG, or PCI; (4) have none of the following safety exclusions: history of kidney stones, renal failure or dialysis, hypercalcemia, hypo-or hyperparathyroidism, severe liver disease (cirrhosis), or sarcoidosis or other granulomatous diseases such as active chronic tuberculosis or Wegener's granulomatosis; (5) have no allergy to fish (for EPA+DHA); (6) have no other serious illness that would preclude participation; (7)

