Fundus Photographs - In order to obtain the highest quality endpoints possible in **VITAL-AMD**, we will obtain standard fundus photographs (e.g. 30° color photographs centered on the macula) of each eye from all participants for whom we confirm a diagnosis of AMD by review of medical records. In our recent experience, nearly all cases of neovascular AMD have photographs, angiograms, or OCTs available as part of routine care, however, dry AMD cases may not have photos. We will take the following steps to obtain photos for each prevalent case at baseline and for all incident cases: 1) When we obtain the medical record information, we will request copies of fundus photos centered on the macula for both eyes if available, or if not available we will ask whether the doctor would be willing and able to obtain a new set of photos for VITAL-AMD. 2) Study participants who do not already have photos in their medical records will be asked whether they would be willing to have photos taken (we have received funds to reimburse clinics for taking and sending photographs for VITAL participants with AMD), 3) If the participant's own doctor is not willing or able to take a set of photographs (e.g. s/he doesn't have the equipment), we will assist participants to obtain photographs from a doctor near their home. We will use databases (e.g. the Academy of Ophthalmology maintains a list by subspecialty) to search for retina specialists or other eye doctors with offices near the study participant and ascertain their willingness to take a set of photos for VITAL-AMD. 4) At the end of the trial, we will obtain a 2nd set of photos from all cases who remain alive and for whom we have not already documented progression to advanced AMD. 5) We will use the simplified AREDS scale to evaluate the photographs (grading will be done masked to randomization status).

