Assessment of AMD progression. - We will send an annual follow-up questionnaire to all participants with medical-record confirmed AMD to ascertain progression to advanced AMD. The questionnaire will ask about changes in the participant's vision, and any updates on their diagnosis of AMD (e.g. the development of the "wet" form, any treatments received [e.g. anti-VEGF therapy], etc.). We will obtain follow-up medical records from all cases in which we suspect progression may have occurred. We will also routinely obtain follow-up records every two years from all participants with confirmed AMD that has not yet progressed to advanced AMD to help ensure no cases of progression are missed. Finally, we will also obtain a second set of retinal photographs at the end of the trial and grade these using the simplified AREDS scale. Progression along the simplified AREDS scale will be ascertained during analysis by comparison of the final grade with the baseline grade.

Validity of medical record-confirmed incident AMD - At initiation of VITAL-AMD we will conduct a pilot study to further validate our methodology for collection of photographs and to estimate sensitivity of case detection in the VITAL population. We will immediately seek to obtain informed consent for review of eye exam records and retinal photographs from a sample of 500 randomly selected VITAL participants at baseline. We will review medical records and photos masked to both randomized treatment assignments as well as the participants' response to the question about a prior diagnosis of AMD. We will estimate sensitivity based on the proportion of true

positives, that is the proportion of true AMD cases (identified by reviewing medical records and photos) that we identified using our methodology for AMD case identification (i.e. those that reported AMD on the baseline questionnaire that were confirmed by review of medical records). With estimated baseline prevalence of AMD=0.07 we will be able to estimate sensitivity with a 95% CI of ±15%. If sensitivity is found to be too low (e.g. <65%), we will consider strategies for increasing case detection in *VITAL-AMD*, for example by increasing participant awareness of AMD and the importance of eye exams for its detection, e.g. through participant newsletters.

V. BIOSTATISTICAL ANALYSIS

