Assuming annual event rates for AMD observed in our previous trials of men and women, and an average follow-up of 6 years (expected for *VITAL*), *VITAL-AMD* will have good (≥80%) to excellent (≥95%) power to detect reductions of ≥20% in the primary AMD endpoint.

The study design is a 2x2 factorial randomized trial. With the large sample size, randomization should assure an equal distribution of known and unknown confounders between treatment groups, but we will control in analysis for any chance imbalances that may occur for AMD risk factors or conditions requiring more frequent medical attention that could increase the likelihood of AMD diagnosis. We will estimate the main treatment effects using the intention-to-treat principle based on randomized treatment assignment. Initial analyses of primary and secondary AMD endpoints will include contingency tables in which the rate of each endpoint (number of events per person-year of observation) among participants allocated to active treatment will be compared with the rate among those allocated to its placebo; controlling by stratification for the other treatment assignment. In addition, Kaplan-Meier survival estimates, the logrank test, and proportional hazards regression models201 will be used to determine whether there is a difference in time to an AMD event. Because an extended exposure to the study agents may be required to observe an effect, we will also conduct analyses which exclude AMD events that occur during the early years after randomization. To address the issue of AMD ascertainment, we will also test associations in models where the at-risk population during each 1 y follow-up period is restricted to those who report having had an eye exam during that year.

We will examine effect modification by the other randomized intervention, by race/skin pigmentation (for vitamin D), and by other risk factors by including an interaction term in proportional hazards models, as well as using methods for testing additive interactions. Stored blood samples will be used to measure genetic polymorphisms and analyses will examine the effect of these polymorphisms on the AMD endpoints, as well as modification of the treatment effects. These analyses will be analyzed as a nested case-control study using multivariable conditional logistic regression analyses and will also include testing of interactions on the additive scale.

VI. RISKS AND DISCOMFORTS

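### Does progression on the simplified AREDS scale, read from two photographs with no event date, leave the planned time-to-event analyses unworkable?

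*Combined protocol and SAP*

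**What the plan says.** Two kinds of progression appear in section IV of the protocol.

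- **Progression to advanced AMD.** Under Assessment of AMD progression, confirmed cases receive a yearly questionnaire, and records are fetched whenever progression is suspected and every two years in any case. Under AMD questionnaire, the date of a neovascular diagnosis is recorded.
- **Movement along the simplified AREDS scale.** "Progression along the simplified AREDS scale will be ascertained during analysis by comparison of the final grade with the baseline grade". Under Fundus Photographs, first photographs are sought for prevalent cases at baseline and for all incident cases, and copies already in the medical record are accepted. For the second set, "we will obtain a 2nd set of photos from all cases who remain alive and for whom we have not already documented progression"; the progression meant there is to the advanced stage.

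Section V, Biostatistical Analysis, applies event rates per person-year to the primary and secondary AMD endpoints, which it does not list. It adds Kaplan-Meier, logrank and proportional hazards methods "to determine whether there is a difference in time to an AMD event". It also plans analyses that "exclude AMD events that occur during the early years after randomization", and models in which "the at-risk population during each 1 y follow-up period is restricted to those who report having had an eye exam during that year".

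The Background speaks of "the primary (incidence) and secondary (progression to advanced stages) prevention of AMD". The Specific Aims define the cases for the genetic analyses as "incident AMD cases and progression to advanced AMD".

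**The concern.** Read together, the two sections seem not to fit. A grade change found by comparing two photographs has no date, whereas a survival curve, an early-event exclusion and a yearly risk set all ask when the event happened. Section V names no interval-censored, ordinal or two-time-point method as an alternative.

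Other details are open too: how old a prevalent case's first photograph may be, which cases enter the comparison, and how deaths, cases already advanced (who have no second set by design) and missing pairs are counted. An old first photograph brings in steps that occurred before randomization and pulls a real effect toward 1. Unequal loss of photographs could create a small false difference. If these choices were made after unblinding, they could be made with the results in view.

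**Working it through.** **Which planned analyses need a date.**

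| Planned analysis | On undated scale steps |
|---|---|
| Rate per person-year | Possible, with photo-to-photo time as time at risk |
| Proportional hazards | Possible in grouped form (complementary log-log) |
| Kaplan-Meier, logrank | Need an interval-censored form |
| Early-event exclusion, yearly eye-exam risk set | Not possible; need dated events |

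The last row is the only true obstacle. Both of those analyses work for incidence and for dated advanced AMD.

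**Illustrative model.** The documents give no progression rates, so all rates here are assumptions. Prevalent cases start unchanged and are followed for 6 years (the average follow-up in section V). Yearly rates are 6% to worse, 1% straight to advanced, 6% from worse to advanced and 1.5% death. Ranges come from 54 combinations of 3/6/9%, 0.5/1/2%, 3/6/10% and 1/2%.

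Placebo after 6 years: unchanged 0.600, worse 0.223, advanced 0.094, dead without advanced AMD 0.082.

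- Graded pairs (alive, not advanced): 0.223 / (0.600 + 0.223) = 0.271.
- Advanced AMD counted as progression: (0.223 + 0.094) / (0.600 + 0.223 + 0.094) = 0.346.

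With a hazard ratio of 0.8 on every step, the active-arm figures are 0.228 and 0.288.

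- Risk ratios: 0.228 / 0.271 = 0.84 (range 0.82 to 0.86) and 0.288 / 0.346 = 0.83.
- Grouped hazard ratio, advanced AMD counted: ln(1 − 0.288) / ln(1 − 0.346) = 0.80, the value put in. It stays at 0.80 in all 54 combinations.

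**Old first photographs.** Taken 1, 2 or 4 years before randomization, they move 0.84 to 0.264 / 0.303 = 0.87, 0.297 / 0.333 = 0.89 and 0.356 / 0.387 = 0.92. Each is a dilution toward 1.

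**Early steps.** If the effect starts only at year 2, graded pairs give 0.243 / 0.271 = 0.90, against 0.163 / 0.197 = 0.83 if the first two years could be excluded. This too is dilution.

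**No drug effect.** Graded pairs give 1.00, if missing photographs do not depend on progression differently by arm. Suppose documented advanced AMD is added, missing pairs are dropped, and 20% (placebo) and 30% (active) of second photographs are missing:

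- placebo (0.8 × 0.223 + 0.094) / (0.8 × 0.823 + 0.094) = 0.362
- active (0.7 × 0.223 + 0.094) / (0.7 × 0.823 + 0.094) = 0.373
- ratio 1.03 (range 1.01 to 1.06)

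With 20% against 22% missing, the ratio is 0.364 / 0.362 = 1.006. Weighting graded pairs up to all living non-advanced cases in their arm restores 1.00.

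**Size of the measure.** At the 7% prevalence given in section IV, 0.07 × 20,000 = 1,400 prevalent cases, or 700 per arm. A two-sided 5% comparison of 0.271 with 0.228 has 46% power at 700 per arm (20% to 70% over the 54 combinations). It has 39% at the 0.823 × 700 = 576 per arm expected to be alive and not advanced.

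**The case for a change.** The strongest case for a change is that the plan loses either way. If section V's unlisted endpoints include scale change, two of its analyses cannot be applied and the others need a form it does not name. If they do not, scale change has no stated method at all. The primary aims ask about incidence and/or progression without limiting progression to advanced disease, so the wider reading is open. Statements about intention to treat and the entire cohort do not settle the matter, because only confirmed cases are photographed and incident cases get their first grade after randomization.

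That last point can matter. Suppose the agent delays onset (hazard ratio 0.6 after year 3, uniform placebo onset) but does nothing to progression at 5% per year. A per-case comparison of incident cases then gives 0.152 / 0.136 = 1.12, because active-arm cases have longer between photographs (3.375 against 3.0 years). Per photo-to-photo year the ratio is about 0.99, so the person-year rate that section V already plans removes nearly all of it.

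The omissions therefore stand as omissions. The claim that proportional hazards cannot be used does not, since the grouped form needs no dates. Nor is there a demonstrated conflict with section V, because it never assigns scale change to its endpoints. Masked data collection and grading, together with the listed steps for obtaining photographs, make a large difference in missing photographs between arms less likely, though they supply no analysis rule.

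**Conclusion.** No change follows. The plan leaves detail unstated for a measure that reads as supplementary: the Background and the case definition in the Aims both mean progression to advanced AMD, and neither that outcome nor incidence depends on the photograph pairs.

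In prevalent cases the choices left open mostly dilute a real effect (0.84 to at most 0.92 with a first photograph 4 years old) and do not create a false one. The exception examined is a ratio of about 1.03, which needs a 10-point difference in missing photographs between arms and a particular way of combining the data. An analyst would ordinarily use a binary, ordinal or grouped model for a two-photograph outcome, keep the date-dependent analyses for dated events, show prevalent and incident cases separately, and report missing pairs by arm.

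The sizes rest entirely on assumed rates, and the 1.00 under no effect rests on the missing-photograph condition given above. The conclusion also rests on scale change being supplementary. If it were presented as the main progression result, the unstated choices would carry more weight.

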Some cross-sectional studies have reported significant inverse associations between higher fish intake and risk of early²¹ or late AMD,²²⁻²⁶ while others found no association.²⁷⁻²⁹ Among studies examining omega-3 fatty acids, 2 studies found no significant relationships, 21, 30 whereas 4 studies showed reduced risks of neovascular AMD²²⁻²⁴ or central geographic atrophy, ²⁵ although in 2 studies the benefit was restricted to those with low dietary intake of linoleic acid. 22, 23 Prospective studies include a report on 567 incident cases of AMD from the Nurses' Health Study (NHS) and Health Professionals Follow-up Study (HPFS) that showed a significant 30% reduction in AMD incidence with high DHA intake (RR not significant after adjustment for other fats).31 High intake of EPA was associated with a non-significant 23% lower risk of AMD. In the Blue Mountains Eye Study, higher intake of omega-3 fatty acids lowered risk of early AMD by 60% after 5 y.32 At 10 y, the reduction was attenuated and not significant.³³ In the Melbourne Collaborative Cohort Study, higher omega-3 fatty acid intake reduced early AMD risk by 15%.34 In the Age-related Eye Disease Study (AREDS), after 6.3 y of follow-up, risks for central geographic atrophy were 45% & 56% lower in those with high intake of DHA & EPA, respectively.35 Higher intakes of DHA & EPA were also associated with ~25% lower risks for progression to advanced AMD after 8 y follow-up in AREDS.36 At 12 y, there continued to be a significant ~30% reduction in risk of advanced AMD for EPA & DHA,³⁷ as well as total intake of omega-3 fatty acids.³⁸ A meta-analysis showed that a high intake of omega-3 fatty acids conferred a 38% risk reduction for advanced AMD, and fish intake ≥2x/wk was associated with 25% and 33% lower risks of early and advanced AMD, respectively.³⁹

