We recently examined dietary intake of omega-3 fatty acids and AMD among 38,022 women in the Women's Health Study (WHS) who completed a dietary questionnaire at baseline and were free of a diagnosis of AMD. A total of 235 cases of visually significant AMD were confirmed during 10 y of follow-up. Women in the highest third of DHA intake had a 38% lower risk of AMD (RR, 0.62; 95% CI, 0.44-0.87) compared to those in the lowest third of intake. High intake of EPA was also associated with a reduced risk of AMD (RR, 0.66; 95% CI, 0.48-0.92). These prospective data from a large population of women appear to be the strongest evidence to date to support a role for DHA and EPA in the primary prevention of AMD.

Possible Mechanisms for Vitamin D in AMD - A plausible role for vitamin D3 in AMD prevention can be postulated due to its immunomodulatory, anti-inflammatory, and antiangiogenic properties. 1,25(OH)2D interferes with the activation and signaling of NF-κB.^{40, 41} 1,25(OH)2D decreases production of proinflammatory cytokines IL-2,42 IL-6,43 IL-8,44 and IL-12,45 increases production of the antiinflammatory cytokine IL-10,46 and regulates expression of matrix metalloproteinase-9.47 Vitamin D also lowers blood levels of C-reactive protein, a marker of systemic inflammation that we have prospectively linked to elevated risks of AMD in the WHS⁴⁸ and others have shown to be associated with AMD.⁴⁹⁻⁵² Vitamin D is a potent stimulator of mechanisms for pathogen elimination, which could be relevant given the possible involvement of chronic infection in AMD.53 In addition, vitamin D regulates the renin-angiotensin-aldosterone system (RAAS) via suppression of renin gene expression and biosynthesis,54 and could exert an indirect beneficial effect on AMD through improved blood pressure control. 55 Favorable effects of vitamin D on glucose tolerance and insulin sensitivity^{56, 57} could also mediate a beneficial effect in AMD as suggested by the association between dietary glycemic index and AMD. 58-62

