In vitro and in vivo studies have demonstrated that 1,25(OH)2D profoundly inhibits growth of a variety of tumors by directly impacting the proliferation and activity of endothelial cells (ECs) and inhibiting angiogenesis, actions mediated by VDR.⁶³⁻⁶⁵ In the mouse oxygen-induced ischemic retinopathy (OIR) model, 1,25(OH)2D-treated animals demonstrated a dose-dependent reduction in retinal neovascularization, and inhibition of retinal EC capillary morphogenesis without a significant inhibitory effect on EC proliferation and migration.⁶⁶

To date, there are 3 studies of vitamin D and AMD, all supportive. Circulating 25(OH)D reflects all sources of vitamin D exposure, has a half-life of 2-3 weeks, and is the most comprehensive and stable indicator of vitamin D status.⁶⁷ Data from the 3rd NHANES indicated that serum levels of 25(OH) D were inversely associated with the prevalence of early AMD (OR for extreme quintiles, 0.64, 95%CI, 0.5-0.8), but not advanced AMD (OR, 1.16, 95%CI, 0.5-3.1).⁶⁸ Data from the Carotenoids and Age-Related Eye Disease Study indicated that high serum 25(OH)D status may be protective against intermediate AMD in women <75 y (OR for extreme quintiles, 0.57; 95% CI, 0.33-0.99; p=0.02).⁶⁹ Recent data from a monozygotic twin study with discordant AMD phenotypes found higher dietary intake of vitamin D in the twin with less severe AMD.⁷⁰

II. SPECIFIC AIMS

The primary aims of this proposal are:

- 1. Does fish oil supplementation (EPA+DHA, 1g/d), compared to placebo, reduce the incidence and/or progression of AMD?
- 2. Does vitamin D3 supplementation (2000 IU/d), compared to placebo, reduce the incidence and/or progression of AMD?

The primary aims will be addressed in analyses involving the entire **VITAL** cohort of n=20,000 older men and women.

The secondary aims of this proposal are:

3. Are there synergistic or antagonistic effects of fish oil and vitamin D3 supplementation on the primary and secondary AMD endpoints?

This secondary aim will be addressed in analyses involving the entire *VITAL* cohort of n=20,000 older men and women.

- 4. Does baseline circulating vitamin D status modify the effect of vitamin D3 supplementation on AMD?
- 5. Does baseline circulating omega-3 fatty acid status modify the effect of EPA+DHA supplementation on AMD?

Secondary aims 4 and 5 will be addressed in the subgroup which provides a baseline blood specimen (N~16000).

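### Does the unnamed primary AMD endpoint in Section V, or the unquantified claim of strong power for progression in Section I, require a change to the plan?

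*Combined protocol and SAP*

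**What the plan says.** Section V gives the plan's only power figure for a treatment effect: the study "will have good (≥80%) to excellent (≥95%) power to detect reductions of ≥20% in the primary AMD endpoint". It rests on AMD event rates from the investigators' earlier trials, which are not printed, and on an average follow-up of 6 years. The section goes on to mention primary and secondary AMD endpoints without listing them.

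Other places bear on what the endpoint is:

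- Section I says the study "will have strong statistical power to address the primary (incidence) and secondary (progression to advanced stages) prevention of AMD".
- Section II, aims 1 and 2, ask whether each agent can "reduce the incidence and/or progression of AMD". It adds: "The primary aims will be addressed in analyses involving the entire" VITAL cohort of 20,000.
- Section II, aims 6 to 8, draw their cases from "all AMD cases (incident AMD cases and progression to advanced AMD").
- Section IV describes medical-record-confirmed AMD, a visually significant case group (acuity 20/30 or worse), neovascular AMD, progression to advanced AMD, and progression on the simplified AREDS scale. None is ranked.

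The one absolute AMD rate that can be worked out comes from Section I, in a cohort study of "omega-3 fatty acids and AMD among 38,022 women": "A total of 235 cases of visually significant AMD were confirmed during 10 y of follow-up".

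**The concern.** A power statement means little until the event is named. The candidates differ in who is at risk: about 7% of participants are expected to have AMD at baseline and cannot have incident AMD, so a whole-cohort analysis fits only a combined event. They also differ in how often the event occurs, and so in whether 80–95% power can hold. An unnamed primary endpoint also leaves room to choose among candidates once results are known.

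For progression the position looks weaker still. Section I calls the power strong, yet no progression rate, expected count or detectable effect appears anywhere. A null progression result might then be read as coming from a well-powered comparison when nothing printed supports that reading.

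**Working it through.** **Inputs from the plan.** 20,000 participants (Section II); 6 years on average and a 20% reduction (Section V); baseline prevalence 0.07 (Section IV, validity pilot); 235 cases in 38,022 women over 10 years (Section I). **Assumed, because not stated:** two-sided 5%, 1:1 allocation for each agent, no dropout, and a placebo progression hazard of 1–5% per year.

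**1. The stated range.** Events needed = 4(z₀.₉₇₅ + z_power)² / (ln HR)², with HR 0.80 and (ln 0.80)² = 0.0498.

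- 80% power: 4(1.960 + 0.842)² / 0.0498 = 631.
- 95% power: 4(1.960 + 1.645)² / 0.0498 = 1,044.

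Over 20,000 × 6 = 120,000 person-years these are 5.3 and 8.7 events per 1,000. Over the 18,600 expected to be free of AMD (111,600 person-years) they are 5.7 and 9.4. The plan's figure cannot be reproduced exactly, because its rate and alpha are not printed. The range may also run over effect sizes: 95% power at HR 0.75 needs 4(3.605)² / (ln 0.75)² = 51.98 / 0.0828 = 628 events, close to the 631 that give 80% at HR 0.80.

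**2. The one printed rate.** 235 / 380,220 = 0.0618% per year. Expected events = 18,600 × 6 × 0.000618 × (1 + 0.8)/2 = 62. Power = Φ(√62/2 × 0.2231 − 1.960) = Φ(−1.08) = 14%. The stated range needs a placebo rate of 631 / (111,600 × 0.9) = 0.63% to 1,044 / (111,600 × 0.9) = 1.04% per year, about 10 to 17 times higher. This does not test the claim. The printed rate is for visually significant AMD only, in women whose ages are not given. VITAL enrols men from 60 and women from 65, and Section V relies on trials of both sexes.

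**3. Incidence alone or combined.** Baseline cases: 0.07 × 20,000 = 1,400. Their progression events at 1–5% per year are added to the 631 or 1,044 incident events. If progression is not slowed, the pooled log hazard ratio is ln 0.80 × incident events / all events.

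| Incident events | Agent slows progression equally | Agent does not slow progression |
|---|---|---|
| 631 (80% power alone) | 84–93% | 75–61% |
| 1,044 (95% power alone) | 96–99% | 93–87% |

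**4. Progression.** Hazards are exponential. With n baseline cases followed for 6 years and m incident cases diagnosed uniformly over 6 years, events in an arm with hazard λ are (n/2)(1 − e^(−6λ)) + (m/2)[1 − (1 − e^(−6λ))/(6λ)]. Example with n = 1,400, m = 631 and a placebo hazard of 3%: placebo 115.3 + 26.8, active (2.4%) 93.9 + 21.7, total 258.

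The 0.07 is the prevalence of true cases, found from records and photographs in the validity pilot: 500 × 0.07 = 35 cases, and 1.96√(0.65 × 0.35/35) = 16%, close to the quoted ±15%. The study itself finds baseline cases by self-report and confirmation, and Section IV gives a sensitivity below 65% as an example of too low. At 65%, 1,400 × 0.65 = 910 would be followed.

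| Baseline cases, incident cases | Events at 1 / 3 / 5% | Power for 20% reduction at 1% and 5% | Reduction detectable with 80% power at 1 / 3 / 5% |
|---|---|---|---|
| 1,400, 631 | 90 / 258 / 409 | 18%, 62% | 47 / 30 / 24% |
| 1,400, 1,044 | 101 / 289 / 460 | 20%, 67% | 45 / 29 / 23% |
| 910, 631 | 65 / 184 / 293 | 14%, 48% | 54 / 35 / 28% |
| 910, 1,044 | 76 / 216 / 344 | 16%, 54% | 51 / 33 / 26% |

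The figures can also move up. If an assumed 20% of incident cases were already advanced at diagnosis and counted as events, power with 1,400 baseline cases would be 37–72% (631 incident cases) or 50–81% (1,044).

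The 20% reduction applied to progression is a choice made for this check, not the plan's. Section I reports for omega-3 intake: "A meta-analysis showed that a high intake of omega-3 fatty acids conferred a 38% risk reduction for advanced AMD". With 1,400 baseline cases, 80% power for a 38% reduction needs a hazard of 1.5–1.7% per year, and for 30% it needs 2.7–3.0%. Both lie inside the assumed range. These are observational intake comparisons, so the support is partial, and Section I gives no comparable figure for vitamin D and progression to advanced AMD.

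**The case for a change.** The strongest case for a change is that the gap is in the text itself. The words primary and secondary in Section I describe kinds of prevention, not ranked endpoints. Even if incidence is primary, the case definition could be any confirmed, visually significant or neovascular AMD, and aims 1 and 2 refer to the whole cohort. Naming the endpoint would cost only a few lines.

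The factual part stands: the endpoint is not named, and the claim of strong power for progression has no number behind it. What does not follow is that the plan must be altered. The arithmetic shows that power depends on the definition, not that the stated range is wrong. Writing in a combined primary endpoint would settle the sponsor's choice against the lean of Sections I and V, and could reduce power. Putting detectable reductions into Section I would enter assumed hazards and an upper-limit case count, and the results shift by 3 to 7 percentage points when 910 cases replace 1,400.

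The worry about choosing late cannot be settled from this document. Masked case review and grading do not by themselves prevent it, but nothing here shows that the choice was left until results were known.

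**Conclusion.** No change is called for. This is a gap that analysts can fill sensibly. Section I pairs primary with incidence and Section V bases power on AMD event rates, so the natural analysis is confirmed incident AMD among people free of AMD at baseline, with progression analysed among confirmed cases. The more specific case groups in Section IV can be reported beside them. Excluding baseline cases from an incidence risk set is ordinary practice and does not conflict with analysis by randomized group.

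The records, photographs and follow-up for every candidate event are already to be collected, so naming one would not alter enrolment or data collection. The stated power needs about 5.3 to 8.7 events per 1,000 person-years, and nothing printed rules that out for a broad case definition.

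For progression, strong is an unsupported adjective. Power for a 20% reduction could be anywhere from 14% to 67% under the main assumptions, and higher if advanced disease at first diagnosis counts. At analysis, the observed event count and confidence interval will show how informative a null result is. All of this assumes two-sided 5%, equal allocation, no dropout and a progression hazard of 1–5% per year.
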